7.1.3 Presentation

The summary statistics, including least squares mean estimates, 95% confidence interval and p-values will be presented using SAS output delivered in Word format.

7.2 Secondary Endpoints

7.2.1 Definitions

- Relative Change in UDysRS total score, calculated from baseline.
- Change in Total Objective Score (III, IV) of the UDysRS from Baseline (Day 1) to Visit 4 (Day 28).
- Change in total daily "OFF" time as assessed by patient completed 24-hour diaries, from run-in to Visit 4 (Day 28).
- Change in Unified Parkinson's Disease Rating Scale (MDS-UPDRS) sum score of parts II+ III (M-EDL+ ME)).
- Change in sum score of Questions 4.1 and 4.2 (dyskinesia) in MDS-UPDRS part IV to Visit 4 (Day 28).

Scale	Component	Attribute
UDysRS	Total Objective Score (III, IV)	Total score
MDS-UPDRS	Part II+III (M-EDL +ME)	Sum score
	Part IV Questions 4.1 and 4.2	Sum score
24-hour patient diaries	OFF time	Total daily hours

7.2.2 Analyses

The change from baseline will be defined as both absolute and percent change.

All Secondary endpoints can be considered quantitative continuous data (Interval in type). As such the Change from baseline to End of Treatment (Visit 4, Day 28 or earlier in the event of withdrawal) will be derived for each patient and analysed using an Analysis of Covariance (ANCOVA) model to compare the two treatment groups (IRL790 vs Placebo).

The ANCOVA analysis will allow estimation of the size of treatment effects as well as magnitude of differences between the active treatment and control (IRL790 - Placebo). The dependent variable will be the Change from baseline value and Treatment group the explanatory (independent) variable and fixed factor. A baseline covariate term will be included to ensure minimum variance unbiased estimation.

Model assumptions will be investigated, and a suitable data transformation or non-parametric equivalent model substituted if appropriate.

Actual p-values and 95% confidence intervals for least square mean estimates of the treatment effects (including differences between active treatment and placebo) will be presented for these models.

7.2.3 Presentation

The summary statistics, 95% confidence interval and p-values will be presented using SAS output delivered in Word format.

7.3 Exploratory Endpoints

- 7.3.1 Definitions
- Unified Parkinson's Disease Rating Scale (MDS-UPDRS), part I (total score), part II (total score), part III (total score) and part IV (total score) from Baseline (Day 1) to Visit 4 (Day 28).
- Unified Parkinson's Disease Rating Scale (MDS-UPDRS) Question 1.2 (Hallucinations and Psychosis) from Baseline (Day 1) to Visit 4 (Day 28).
- Unified Parkinson's Disease Rating Scale (MDS-UPDRS) Question 1.6 (Features of dopamine dysregulation syndrome) from Baseline (Day 1) to Visit 4 (Day 28).
 - Change in sum score of Questions 4.3, 4.4 and 4.5 (motor fluctuations) in MDS-UPDRS part IV to Visit 4 (Day 28).
 - Change in sum score of Questions 3.15 and 3.16 (postural and kinetic tremor of the hands) in MDS-UPDRS part III to Visit 4 (Day 28).
- Unified Parkinson's Disease Rating Scale (MDS-UPDRS) Question 4.3 (Time spent in the off state) from Baseline (Day 1) to Visit 4 (Day 28).
- Unified Parkinson's Disease Rating Scale (MDS-UPDRS) Question 4.6 (Painful off state dystonia) from Baseline (Day 1) to Visit 4 (Day 28).
- Clinician's Global Impression of Change in overall PD symptoms at Visit 4 (Day 28).
- Change in "ON" time with troublesome dyskinesia as assessed by patient completed 24hour diaries, from run-in to Visit 4 (Day 28).
- Change in "ON" time as assessed by patient completed 24-hour diaries, from run-in to Visit 4 (Day 28).
- Change in Sleep time as assessed by patient completed 24-hour diaries, from run-in to Visit 4 (Day 28).

The change from baseline will be defined as both absolute and percent change.

7.3.2 Analyses

The Exploratory endpoints (except CGI) can be considered quantitative continuous data (Interval in type). As such the Change from baseline to End of Treatment (Visit 4, Day 28 or earlier in the event of withdrawal) will be derived for each patient and analysed using an Analysis Of Covariance (ANCOVA) model to compare the two treatment groups (IRL790 vs Placebo).

The ANCOVA analysis will allow estimation of the size of treatment effects as well as magnitude of differences between the active treatment and control (IRL790 - Placebo). The dependent variable will be the Change from baseline value and Treatment group the explanatory (independent) variable and fixed factor. A baseline covariate term will be included to ensure minimum variance unbiased estimation.

Model assumptions will be investigated, and a suitable data transformation or non-parametric equivalent model substituted if appropriate.

Actual p-values and 95% confidence intervals for least square mean estimates of the treatment effects (including differences between active treatment and placebo) will be presented for these models.

The CGI will be analysed using Chi-square test without continuity correction.

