The CGI (an exploratory efficacy variable) however is categorical data which is ordinal in nature and will be analysed using the Van Elteren hypothesis test.

Pharmacokinetic (PK) assessments

PK variables measured in plasma are: IRL790 parent drug and two of its metabolites (IRL902 (n-dealkylated) and IRL872 (acetylated)). In addition, the biomarker P-Prolactin is also measured.

Samples are obtained pre-dose and 2h post dose (C_{max}) on Day 1 and Day 28 and will be summarised as interval data. If appropriate, these will be presented overall for the IRL790 treated group but also according to IRL dose.

To assess the relationship between the treatment doses (7.5mg b.i.d. upwards) and drug plasma concentration a polynomial regression model to fit dose or log(dose) vs plasma concentration for each variable and sampling time will be used. However, this is dependent on the number of patients in each of the dose groups of this maximum tolerated dose (MTD) investigation.

Safety assessments

Safety evaluations include: Adverse events and Concomitant medications reporting, Complete physical examination, Vital signs, ECG (12 lead) and Clinical safety laboratory tests (clinical chemistry, haematology and coagulation). All will be presented as data summaries. No formal statistical analyses will be performed.

Adverse events (Overall, By seriousness, By severity, By relationship) and Concomitant medications (Overall) recorded throughout the investigation will be reported following classification according to MedDRA (SOC/PT) and WHODD (ATC Level 2.4) dictionaries respectively.

All other safety evaluations are performed at Screening, Day 28 (Visit 4 or at Withdrawal) and Follow-up (5-8 days after Visit 4) and will be summarised accordingly.

Safety laboratory samples assayed at the local hospital will be presented as interval summaries according to Site.

SAFETY

Recruitment:

The DSMB will convene after 20 and 40 patients have completed the Follow-Up visit (with adequate safety assessment data) for a formal safety review.

Note that recruitment will continue throughout the 20 and 40 patient DSMB

Data Safety Monitoring Board

The DSMB will convene under the following circumstances:

- The DSMB must meet once the 20th and 40th patient has completed the Follow-Up visit
- The DSMB must meet as soon as there has been a SUSAR

The DSMB has the right to recommend to the Sponsor that the study be suspended, terminated or lower doses be given, if considered appropriate.

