8.2.2.7. Clinical Global Impression of Change (CGI-C)

The CGI-C will be administered at the Visit 4 (Day 28 End of Treatment or earlier in the event of withdrawal). The Investigator will rate on a 7-grade scale how, in their judgment, the patients' global clinical condition has changed from baseline. (See [Appendix 4 Clinical Global Impression of Change \(CGI-C\)](#))

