11.9. Efficacy Analyses

All Primary, Secondary and Exploratory endpoints (except CGI) can be considered quantitative continuous data (Interval in type). As such the Change from baseline at and at End of Treatment (Visit 4, Day 28 or earlier in the event of withdrawal) will be derived for each patient and analysed using an Analysis Of Covariance (ANCOVA) model to compare the two treatment groups (IRL790 vs Placebo).

The ANCOVA analysis will allow estimation of the size of treatment effects as well as magnitude of differences between the active treatment and control (IRL790 - Placebo). The dependent variable will be the Change from baseline value and Treatment group the explanatory (independent) variable and fixed factor. A baseline covariate term will be included to ensure minimum variance unbiased estimation.

In view of the small sample size and relatively large number of sites there are insufficient degrees of freedom to include Site as a factor in the model.

Model assumptions will be investigated and a suitable data transformation or non-parametric equivalent model substituted if appropriate.

Actual p-values and 95% confidence intervals for least square mean estimates of the treatment effects and differences from placebo will be presented for these models.

The CGI exploratory endpoint is the only other type of data collected. This qualitative and ordinal categorical variable will be analysed using the Van Elteren non parametric hypothesis test (equivalent to Cochran Mantel-Haenszel test with modified ridits (CMH-row mean scores differ). Statistical significance (p-values) for differences between the two Treatment groups (IRL790, Placebo) will be reported together with the actual response proportions.

11.10.Safety Analyses

Safety evaluations include: Adverse events and Concomitant medications reporting, Complete physical examination, Vital signs, ECG (12 lead) at rest and Clinical safety laboratory tests (clinical chemistry, haematology and coagulation).

Adverse events and concomitant medications are recorded throughout the investigational period with the rest performed at Screening, Day 28 (Visit 4 or at Withdrawal) and Follow-up (5-8 days after Visit 4).

All safety laboratory samples are assayed at the local hospital.

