2 INTRODUCTION

This Statistical Analysis Plan (SAP) gives details regarding the statistical analyses and data presentation outlined in the final Clinical study protocol (CSP) for the study *IRL790C003_Protocol_V36_14Nov1714Jan2019*. Any changes from the final CSP are given in Section 8.

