4.4 Summary Statistics

In general, all data collected will be presented with summary statistics and given in patient data listings. Summary statistics will include at least number of patients, mean, standard deviation, median, minimum and maximum for continuous data and frequency and percentage for categorical data. Tables with summary statistics will be divided by treatment group and dose group and visit where applicable. Patient data listings will be sorted by treatment, subject and timing of assessments.

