4.9 Multicenter Studies

No adjustment or analyses for site will be applied.

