8 CHANGES FROM THE CSP

Clinician's Global Impression of Change in overall PD symptoms is assessed at Visit 4 (Day 28) only, and there is hence no comparison from baseline (Day 1) to Visit 4 (Day 28) as stated in the Clinical Study Protocol..

Change in total score of MDS-UPDRS part II+III has been included as a secondary endpoint.

Change in total score of MDS-UPDRS part II, and change in total score of UPDRS part III, have been added as exploratory endpoints.

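### SAP 7.3.2 replaces the protocol's ordinal CGI-C test with a chi-square test, does not declare the change in Section 8, and does not define the table or cut-point

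*SAP*

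**What the plan says.** **Protocol.** Section 8.2.2.7 sets up the measure: "The Investigator will rate on a 7-grade scale how" the patient's overall condition has changed. Appendix 4 lists the grades from marked improvement to marked worsening. The synopsis says the CGI "is categorical data which is ordinal in nature and will be analysed using the Van Elteren hypothesis test". Section 11.9 repeats this ("This qualitative and ordinal categorical variable will be analysed using the Van Elteren non parametric hypothesis test"), equates the test with CMH row mean scores using modified ridits, and adds that response proportions will be reported.

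**SAP.** Section 7.3.2 has one sentence on the test: "The CGI will be analysed using Chi-square test without continuity correction". Section 7.3.1 lists the endpoint as the CGI-C at Visit 4, with no responder definition and no grouping of grades.

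**Declaration of changes.** SAP Section 2 says: "Any changes from the final CSP are given in Section 8". Section 8 does discuss this endpoint, but only to record that "Clinician's Global Impression of Change in overall PD symptoms is assessed at Visit 4 (Day 28) only" and so has no baseline comparison. It says nothing about the test.

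**Related text.** SAP 4.9 states: "No adjustment or analyses for site will be applied". SAP 4.4 promises "frequency and percentage for categorical data", so the distribution of grades by arm will be shown whatever test is used.

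**The concern.** There are three separate problems.

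1. *The hypothesis test is different.* Row mean scores use the order of the grades. A Pearson chi-square on all seven grades gives the same value if the grades are shuffled, so it spreads its sensitivity over six degrees of freedom instead of aiming it at a shift towards improvement.
2. *The change is silent.* A reader who relies on Section 8, which does discuss the CGI-C, would conclude that the protocol's test still stands.
3. *The test is not fully specified.* A continuity correction normally belongs to a 2x2 table, so ruling it out hints at a dichotomy, yet no cut-point appears anywhere. Without a dichotomy the table is 2x7 and sparse, and there is no rule for sparse cells.

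At stake is the one CGI-C p-value. Its result depends on a grouping that the SAP leaves open, and that could therefore be settled after unblinding. Either reading also gives up power against the protocol's test when the effect is a shift across grades.

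**Working it through.** **Inputs from the documents.** Seven ordered grades; 37 per arm (protocol 11.2, SAP 4.1); two-sided 5%. The documents state no power, distribution or effect for the CGI-C, so there is no CGI-C figure to reproduce. The sample size is for the UDysRS: at effect size 0.67 the two-sample t-test needs 35.96, so 36 per arm, and 37 per arm gives 81.1% power, consistent with the stated 80%. Only the 37 is carried forward.

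**Sparseness.** The average expected count in a 2x7 table is 37/7 = 5.3 per cell, so any unevenness across grades takes cells below 5.

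**Constructed example.** Invented counts, marked improvement to marked worsening: active 3/8/12/9/3/2/0, placebo 1/4/8/13/6/4/1. Grade totals are 4, 12, 20, 22, 9, 6, 1.

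- *2x7 Pearson.* With equal arms the statistic is the sum of (a-b)²/(a+b): 4/4 + 16/12 + 16/20 + 16/22 + 9/9 + 4/6 + 1/1 = 6.53 on 6 df, p = 0.37. Four grades have totals below 10, so 8 of 14 expected counts are below 5.
- *Ordinal (Wilcoxon / row mean scores).* Midranks are 2.5, 10.5, 26.5, 47.5, 63, 70.5, 74. The active rank sum is 1167 against an expected 37×75/2 = 1387.5. The tie-corrected variance is 37²/(74×73) × 31986.5 = 8106, SD 90.0. z = 220.5/90.0 = 2.45, p = 0.014.
- *2x2, any improvement.* 23/37 against 13/37: 74(23×24 - 14×13)²/(37×37×36×38) = 5.41, p = 0.020.
- *2x2, moderate or better.* 11/37 against 5/37: 74(11×32 - 26×5)²/(37×37×16×58) = 2.87, p = 0.090.
- *2x2, marked only.* 3/37 against 1/37: 74(3×36 - 34×1)²/(37×37×4×70) = 1.06, p = 0.30.

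**Power by simulation.** 40,000 trials per scenario. Assumed placebo distributions in %, best to worst grade: 2/8/20/45/15/8/2; 5/15/30/30/12/6/2; 8/14/18/25/17/12/6; 3/12/25/40/14/5/1; and flat. The active arm has the log odds of being at or better than each grade raised by ln(OR). Ranges are across the five distributions.

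| Odds ratio | Chi-square 2x7 | 2x2 any improvement | Ordinal |
|---|---|---|---|
| 2 | 14-18% | 29-31% | 36-39% |
| 2.5 | 26-31% | 46-49% | 57-60% |
| 3 | 39-43% | 60-63% | 72-75% |
| 5 | 78-80% | 88-92% | 96-97% |

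With a moderate-or-better cut, power at odds ratio 2.5 is 29-46%.

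**Under no effect.** Rejection is 3.3-4.6% for 2x7, 4.6-4.9% for any improvement and 4.7-5.1% for the ordinal test. The moderate-or-better cut gives 4.6-5.9%. Between 38% and 58% of non-empty 2x7 cells have an expected count below 5.

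**Other assumed distributions.** Three different placebo distributions (2/6/17/45/20/7/3; 2/5/22/45/15/8/3; 5/12/28/35/12/5/3; 20,000 trials each) at odds ratio 3.3 give 45-47% for 2x7 and 79-81% for the ordinal test. The 2x2 cuts give 68-70% (any improvement), 39-62% (moderate or better) and 11-32% (marked only).

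**The case against.** The best defence of the SAP has four parts.

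- **The table is not really open.** Section 7.3.1 defines the endpoint as the CGI-C itself, and the generic categorical shell, Table 12.1-1, shows global-impression grades ungrouped. The natural reading is then the full table, with the remark on continuity correction meaning only the plain Pearson statistic. This has some force, and a post-hoc choice of cut is a possibility, not something the SAP provides for. But the shell is a display template: its visit label and its first grade label do not match this trial, and it does not say what is tested. If the full table is meant, the power loss is at its largest.
- **The protocol's test could not be run as named.** Van Elteren is a stratified test, no strata are defined, and SAP 4.9 excludes site. Some clarification was needed, and protocol Section 11 leaves detailed methods to the SAP. That explains a change, but not dropping the ordinal method without listing it.
- **The power figures are assumed throughout.** They are, and a proportional-odds shift favours a rank test. They support direction and rough size only. Likewise, the 2x7 test is conservative mainly when grades are sparse; it is near nominal when all seven grades are used evenly.
- **The endpoint is exploratory,** there is no multiplicity control, and the frequencies by arm will show direction anyway. All true, and this limits the weight of the point. The SAP still plans a p-value, so the test behind it must be defined.

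**Conclusion.** The concern holds. Three facts can be read from the text without any assumption: the test differs from the protocol's, Section 8 does not declare it, and neither the table nor a cut-point is defined. The undeclared change of test is the firmest of these.

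The cost in power is conditional on 37 CGI-C values per arm, the assumed placebo distributions and a proportional-odds shift. On those terms the 2x7 chi-square keeps about 46-58% of the ordinal test's power at odds ratios 2.5-3 and 81-84% at 5. The any-improvement split keeps 80-86% and 91-95%. The example shows that the unstated choice alone can move a result across 0.05.

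The effect is confined to one exploratory p-value. The primary and secondary analyses and the 74-patient sample size are not affected. It should be corrected because the SAP's version is the weaker analysis and the correction is nearly free.

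**What to change.** Replace the CGI sentence in SAP 7.3.2 with text to this effect:

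> CGI-C at Visit 4 will be compared between IRL790 and placebo on all seven ordered grades with the unstratified Wilcoxon rank-sum test (CMH row mean scores, modified ridits), and presented with the proportion of patients in each grade by arm.

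Do not simply restore the name Van Elteren, because no strata exist for it. A short note in Section 8 that the test is run unstratified would make the link to protocol 11.9 clear.

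If a chi-square test is kept in any form, list it in Section 8 with the reason, and state before unblinding whether the table is 2x7 or 2x2. Give the cut-point if it is 2x2, and a sparse-cell rule if it is 2x7.

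The cost is one sentence in 7.3.2 and one line in Section 8, with no new data. The trade-off is that a rank test is less sensitive to a difference in spread without a shift; the proportions by arm would still show that.

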7.3.3 Presentation

The summary statistics, 95% confidence interval and p-values will be presented using SAS output delivered in Word format.

7.4 PK Endpoints

Plasma concentrations of IRL790 and its metabolites IRL872 and IRL 902 in samples obtained pre-dose and 2h post dose (Cmax) on Day 1 and Day 28 will be summarized, as interval data (using number (n), arithmetic mean, standard deviation (SD), minimum and maximum value, median, geometric mean and coefficient of variation (CV%)) by Day and time-point. If appropriate these will be presented overall for the IRL790 treated group but also according to IRL dose.

7.4.1 Definitions

All absolute and percent change in plasma concentration will be calculated as 2 hour value – pre-dose value.

7.4.2 Analyses

The absolute and percent change will be analyzed using Wilcoxon Rank Sum test.

7.4.3 Presentation

The summary statistics will be presented using SAS output delivered in Word format.

7.5 Safety Endpoints

7.5.1 Physical Examinations

Physical examination results will be categorically summarised as the number and percentage of patients according to treatment group and assessment day.

7.5.2 Vital signs

For blood pressure and pulse rate, Actual values and Change from Screening will be summarized with descriptive statistics, by treatment group and assessment day. Categorically classified (Normal/Abnormal) results will also be summarized.

In addition, Weight measured at Follow up following Screening will be summarised with descriptive statistics for Actual values and Change from Screening by treatment group.

7.5.3 ECG (12-Lead) At Rest

ECG variables will be summarised according to Actual values and Change from Screening using summary statistics and will be presented by treatment group and assessment visit. Categorically classified (Normal/Abnormal) results will also be summarised.

7.5.4 Safety laboratory

All haematology, clinical chemistry and coagulation laboratory tests will be summarised using listings for Actual values and Change from Screening and presented by treatment group and assessment day for each Hospital site separately (due to assays performed locally).

Additionally, the local laboratory normal ranges will be used to classify the results as: High, Normal or Low and categorical summaries presented overall according to treatment group and assessment visit. Pooling across all sites is possible here due to the categorical classification.

